6.1.1. Detailed Administration Guidelines (Part C Only)

Side effects should be anticipated with dinutuximab administration and may occur even with use of pretreatment medications. The need to slow, pause, or even discontinue infusion should be anticipated and is not unexpected. See Section 6.5.3 for guidance for supportive management of anticipated dinutuximab-associated toxicities.

Days 2-5

Administer premedications as outlined in Sections 6.1.4 and 6.5.3.

Hour 0: Administer abemaciclib and temozolomide.

Hour 1: Administer irinotecan over 90 minutes and simultaneously begin normal saline bolus of 10-20 mL/kg.

Hour 2.5: Begin dinutuximab infusion. Start infusion rate at 0.88 mg/m²/hour for the first 30 minutes.

Hour 3: If starting rate is tolerated, increase dinutuximab infusion rate to 1.75 mg/m²/hour. If not tolerated, see Section 6.5.3 for management guidelines

Note: The infusion should be completed at Hour 10, but may be extended for anticipated toxicities, such as uncontrolled pain, fever, hypotension, and tachypnea. The maximum infusion duration is 20 hours; the infusion MUST be stopped at 20 hours even if total planned dose has not completed. The infusion duration and dose delivered must be recorded.

Important Note: Monitoring guidelines should be followed DURING dinutuximab infusion (see Section 6.1.1.1 immediately below).

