Appendix 8). ^{CCI} [REDACTED]

Refer to the Abemaciclib Dosing Charts in Section 10.8 (Appendix 8) for the dose rounding rules based on a patient's BSA for each dose level and if using granules, the number of granules required for each dose.

Participants taking oral granules should follow the provided instructions for the dispensing device and administration.

Until PK samples are completed on Cycle 3 Day 1, participants may only switch abemaciclib formulations (tablets to granules or vice versa) if necessary for a dose adjustment or BSA change. Following the last PK sample, participants may switch formulations as necessary (for reasons other than dose adjustment or BSA change). Oral granules and tablets can never be combined to make up a single dose.

If instructions have been provided to prepare abemaciclib in food/liquid, no other medications should be added to the food/liquid with abemaciclib.

For each cycle, the actual dose administered for all study drugs must be within 10% of the planned dose; any total cycle dose exceeding $\pm 10\%$ from the planned dose for the cycle will result in a protocol deviation. Please contact the Lilly CRP/CRS to discuss any questions for individual situations.

Investigational drugs (including abemaciclib, dinutuximab, GM-CSF, irinotecan, and temozolomide) will be supplied per local laws and regulation and country requirements.

Abemaciclib doses will be administered at approximately the same times on each day. Please see Section 10.8, Appendix 8 (Abemaciclib Dosing Chart) to determine if a change in BSA necessitates a change in abemaciclib dosing.

The planned duration of treatment is not fixed; participants will remain on study until disease progression, unacceptable toxicity, or patient withdrawal (see Section 7.1). Continuation beyond Cycle 12 will be up to the investigator's discretion and should be discussed with the Lilly.

The following treatments will be administered in 21-day cycles. Refer to Sections 1.3.1 and 1.3.2 for the daily schedule.

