- **Abemaciclib** BID orally on Days 1 through 21 according to the dosing tables below. Doses should be separated by at least 6 hours. Abemaciclib should be swallowed whole (refer to Section 6.1.2 for patients with swallowing difficulties). Participants taking oral granules should follow the provided instructions for the dispensing device and administration. If a dose is missed, the patient should take the next dose at its scheduled time. If a participant spits out or vomits abemaciclib within 15 minutes of ingestion, repeat the dose. If vomiting occurs a second time, the dose should not be repeated.

Abemaciclib is authorized in the EU as defined by the EU clinical trial regulation and is not used according to EU authorization in this study.

- **Temozolomide** once daily orally on Days 1 through 5 according to the dosing tables below. For Parts A and C, take temozolomide approximately 1 hour prior to irinotecan. Temozolomide can be taken at the same time as the abemaciclib dose. Temozolomide should be taken on an empty stomach. Temozolomide should be taken according to local standard of care (refer to Section 6.1.2 for patients with swallowing difficulties). If a participant spits out or vomits temozolomide capsule(s) within 15 minutes of ingestion, repeat the dose. If participant vomits temozolomide capsule(s) a second time, the dose should not be repeated. In Part C, IV temozolomide may be allowed if locally sourced and approved by the Lilly CRP/CRS. IV temozolomide should be administered over approximately 90 minutes or per institutional standards. A minimum of 20 hours between temozolomide doses is recommended.

Temozolomide is authorized in the EU as defined by the EU clinical trial regulation and is not used according to EU authorization in this study.

- **Irinotecan (Parts A and C Only)** once daily as IV infusion on Days 1 through 5 according to the dosing table below. A minimum of 20 hours between irinotecan doses is recommended.

Irinotecan is authorized in the EU as defined by the EU clinical trial regulation and is not used according to EU authorization in this study.

- **Dinutuximab (Part C Only)** once daily as an IV infusion over 10 hours on Days 2 through 5. Infusions may be extended to a maximum of 20 hours. The dinutuximab infusion should follow irinotecan. Held doses of dinutuximab are not made up. See Section 6.1.1 for detailed administration guidelines.

Dinutuximab is not authorized in the EU.

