- ^b One dose level higher than the MTD of abemaciclib in Part A (or 115 mg/m² if this was the MTD_A) will serve as the starting dose of abemaciclib in Part B.
- ^c Cohort B5 will only take place if the following occur:
 - 1) The MTD of abemaciclib is not reached when dosed at 115 mg/m² BID in combination with 100 mg/m²/day temozolomide in Part B; OR
 - 2) If abemaciclib 115 mg/m² BID is the MTD for Part A. In this case, Part B will directly start with Cohort B5 using abemaciclib 115 mg/m² BID and temozolomide 150 mg/m²/day.
- ^d Expansion cohorts will enroll 6 patients initially. Additional patients can be enrolled if necessary to confirm safety. Examples may include testing a lower dose in 6 additional patients if DLTs are experienced by at least 2 of 6 patients in the initial expansion cohort or to further confirm tolerability of prolonged treatment.

Part C: Combination Dosing

Part C Dosing Schedule							
	Day 1	Day 2	Day 3	Day 4	Day 5	Days 6-12	Days 13-21
Abemaciclib PO 55 mg/m ² BID x 21 days ^{a, b}	X	X	X	X	X	X	X
Temozolomide PO 100 mg/m ² /day x 5 days	X	X	X	X	X		
Irinotecan IV 50 mg/m ² /day x 5 days	X	X	X	X	X		
Dinutuximab IV 17.5 mg/m ² /day x 4 days		X	X	X	X		
GM-CSF SubQ 250 µg/m ² /day x 7 days						X	

Abbreviations: BID = twice daily; GM-CSF = granulocyte-macrophage colony-stimulating factor; IV = intravenous; PO = orally; MTD_A = Part A maximum tolerated dose; SubQ = subcutaneous.

^a 30 mg/m² may be evaluated due to excessive toxicities, if necessary, as described in Section 4.1.2.

^b An intermediate dose level (ie: between 55 mg/m² and 30 mg/m²) may be explored based on emerging data.

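### In Part C, completing dinutuximab at Hour 10 does not fit Section 6.1.1's own clock: the stated start and rates end at Hour 12.75, and no other time origin is given for Hour 10

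*Protocol*

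**What the plan says.** Protocol Section 6.1.1 gives the Days 2 to 5 sequence for Part C as a list of hours:

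- "Hour 0: Administer abemaciclib and temozolomide"
- "Hour 1: Administer irinotecan over 90 minutes", so irinotecan ends at Hour 2.5
- "Hour 2.5: Begin dinutuximab infusion", at 0.88 mg/m²/h for the first 30 minutes
- at Hour 3, if the starting rate is tolerated, "increase dinutuximab infusion rate to 1.75 mg/m²/hour"

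A note under the list says "The infusion should be completed at Hour 10". It allows extension for anticipated toxicities, and it sets a maximum infusion duration of 20 hours, at which the infusion must stop.

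Section 6.1 describes dinutuximab as given "once daily as an IV infusion over 10 hours on Days 2 through 5", extendable to 20 hours. The Part C dosing table there has a row beginning "Dinutuximab IV 17.5 mg/m", which gives 17.5 mg/m² per day for four days. Section 6.1 also requires that, for each cycle, "the actual dose administered for all study drugs must be within 10% of the planned dose", and it makes a total cycle dose more than 10% away from plan a protocol deviation.

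**The concern.** Every Hour label in the list counts from the oral dose. Read on that clock, the completion hour leaves 7.5 hours for an infusion that starts at Hour 2.5. That is shorter than the 10 hours in Section 6.1 and too short for the dose at the stated rates.

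This is a bedside instruction, and a site has three ways to act on it:

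- stop at Hour 10 with part of the dose not given;
- exceed the stated rate in order to finish by Hour 10;
- keep to the stated rates and run past the stated completion time, although anticipated toxicities are the only ground for extension that Section 6.1.1 names.

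The first affects delivered dose and can become a protocol deviation. The second bears on safety, for a drug whose infusion reactions the protocol expects. The third makes an uneventful infusion look like one prolonged for toxicity. Sites that choose differently would also give the same regimen differently.

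**Working it through.** **Inputs.** The daily dose is 17.5 mg/m² (Section 6.1, Part C dosing table). The start is Hour 2.5, the first rate is 0.88 mg/m²/h for 0.5 h, the rate from Hour 3 is 1.75 mg/m²/h, and the stated completion is Hour 10 (all Section 6.1.1). The stated duration is 10 h (Section 6.1).

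**Trying to reproduce Hour 10.**

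1. Given in the first 30 minutes: 0.88 × 0.5 = 0.44 mg/m².
2. Remaining: 17.5 − 0.44 = 17.06 mg/m².
3. Time for the remainder: 17.06 / 1.75 = 9.75 h.
4. Total duration: 0.5 + 9.75 = 10.25 h.
5. End on the printed clock: 2.5 + 10.25 = Hour 12.75.

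The stated Hour 10 is not reproduced. The gap is 12.75 − 10 = 2.75 h per infusion.

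**Reading 1: Hour 10 counted from the oral dose.**

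- Infusion time available: 10 − 2.5 = 7.5 h.
- Given by then: 0.44 + 7 × 1.75 = 12.69 mg/m², and 12.69 / 17.5 = 72.5%.
- Not given: 17.5 − 12.69 = 4.81 mg/m².
- Average rate from Hour 3 needed to finish: 17.06 / 7 = 2.44 mg/m²/h, which is 1.39 times the stated 1.75.

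**Reading 2: ten hours after the infusion starts (Hour 12.5 on the printed clock).**

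- Given by then: 0.44 + 9.5 × 1.75 = 17.065 mg/m², and 17.065 / 17.5 = 97.5%.
- Gap to completion: 10.25 − 10 = 0.25 h.

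**Sensitivity.** With an unrounded starting rate of 0.875 mg/m²/h, the end is still Hour 12.75 and the share given at Hour 10 is still 72.5%. With a flat 1.75 mg/m²/h and no slow start, the infusion ends at Hour 12.5, and 7.5 × 1.75 / 17.5 = 75.0% is in at Hour 10. Neither variant completes the dose by Hour 10 on the printed clock.

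**Effect on the 10% rule under Reading 1.** The planned cycle total is 4 × 17.5 = 70 mg/m². The shortfall by number of infusions stopped at Hour 10 is:

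| Infusions stopped | Shortfall (mg/m²) | Share of cycle dose |
|---|---|---|
| 1 | 4.81 | 6.9% |
| 2 | 9.62 | 13.7% |
| 4 | 19.24 | 27.5% |

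One truncated infusion stays within the tolerance. Two or more breach it.

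**The case against.** The best defence is that Hour 10 was meant as infusion time. It stands in a note about the infusion, not in the list of hours, and the note goes on to speak of infusion duration. Section 6.1 has the same pair of figures, 10 hours extendable to 20. On that reading only the quarter-hour from the slow start is left. This is plausible and may well be what was intended. But the text does not say that the origin changes, and the same word counts from the oral dose throughout the list directly above. A reader has to guess.

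It is also fair to say that the completion hour is worded as a target and not as an order to stop. The only mandatory stop is at 20 hours, and no rate above 1.75 mg/m²/h is stated. Many sites would probably run the stated rates until the dose is in, and Section 6.1 permits extension without naming a reason. That makes under-dosing less likely. It does not remove the conflict within Section 6.1.1.

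Three stronger readings might be inferred, and the documents do not support them:

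- **The 20-hour limit also lacks an origin.** It does not. Section 6.1.1 calls it an infusion duration, and Section 6.5.3.1 counts it from initiation of the infusion.
- **Any stop at Hour 10 breaks the 10% rule.** The deviation is defined on the total cycle dose, and one such infusion costs 6.9%.
- **The objective response rate or DLT evaluability is compromised.** The first would need repeated truncation, which nothing in the documents shows, and Section 6.1.1 requires the delivered dose to be recorded, so a shortfall would be visible. The second would need the 75% threshold in Section 4.1.1 to mean amount delivered, which is not stated.

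**Conclusion.** The point holds as an internal inconsistency in a dosing instruction. On the clock that Section 6.1.1 prints, its start hour and rates put completion at Hour 12.75 and not Hour 10. The mismatch is 2.75 hours per infusion on that clock, with 72.5% of the dose given at Hour 10. It is 0.25 hours, with 97.5% given, if Hour 10 means ten hours of infusion. Both figures assume an uninterrupted infusion of 17.5 mg/m² with the rate increase at Hour 3. The arithmetic is firm. How sites act on the text is not known, so the effect on delivered dose is a possibility and not a finding. No view is taken here on which time or rate is correct.

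**What to change.** The sponsor should reconcile four items across Sections 6.1 and 6.1.1: the dinutuximab start hour, the two rates, the 10-hour duration and the Hour 10 completion. The completion sentence should state its time origin. The 20-hour limit can stay as it is. The cost is one line in the protocol and a memo to Part C sites. No analysis changes.

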6.1.1.1. Monitoring Guidelines During Dinutuximab Infusion (Days 2-5)

Vital signs should be assessed every 15 minutes for the first hour of infusion, then hourly if stable. More frequent assessment may be required based on the patient's clinical condition. Between dinutuximab infusions, vital signs should be measured every 4 hours at a minimum.

Strict measurement of intake and output is required on Days 2-5.

Daily physical exams, including pupillary reflexes and extraocular movement evaluation, are required before each daily infusion.

Weigh patients daily to assess fluid status. Use diuretics with extreme caution.

See Section 6.5.3 for guidance for supportive management of anticipated dinutuximab-associated toxicities.

6.1.2. Patients with Difficulty Swallowing After Initiating Treatment

If a patient has difficulty swallowing after initiating study treatment, the following should be considered. In all cases, the method of administration should be documented on the CRF.

- For abemaciclib, the Medication Alternative Administration Guide provides instructions for dispersing tablets for oral administration as well as dispersing tablets/granules for NG/G-tube administration. Patients unable to swallow tablets may also switch to oral granules (Part C only) (refer to Oral Granule Dispensing Device and Administration Training Video and Oral Granules IFU).
- For temozolomide, follow standard of care for alternative administration (Trissel et al. 2006; CCLG 2016).

6.1.3. Criteria to Begin Subsequent Cycles of Treatment

To begin dosing at each cycle, the following criteria must be fulfilled. If a patient has not met the criteria to start the next cycle, and the toxicity does not warrant an abemaciclib dose hold per Section 6.6.1.1 (Parts A and B) or Section 6.6.1.3 (Part C), the investigator may use his/her discretion to hold abemaciclib while waiting for the toxicity to resolve. The dose hold should be recorded in the eCRF. A cycle may begin 1 day early (i.e. Day 21) if needed for logistical reasons if all Day 1 criteria are satisfied.

- Absolute neutrophil count $\geq 750/\text{mm}^3$
 - Parts A and B: G-CSF is not permitted within the past 48 hours
 - Part C: G-CSF is not permitted
- Platelets $\geq 75,000/\text{mm}^3$ (platelet transfusion is not permitted within the past 72 hours)
- Total bilirubin $\leq 1.5 \times$ upper limit of normal (ULN), except patients with documented history of Gilbert Syndrome who must have a total bilirubin level of $< 3.0 \times \text{ULN}$
- AST and ALT $\leq 3.0 \times \text{ULN}$, or $\leq 5 \times \text{ULN}$ if the transaminase elevation is due to liver metastases
- For parts A and B, patients must weigh $\geq 10 \text{ kg}$ and have BSA $\geq 0.5 \text{ m}^2$
- For part C, patients with a starting abemaciclib dose of $30 \text{ mg}/\text{m}^2 \text{ BID}$, BSA must be $\geq 0.3 \text{ m}^2$
- Any nonhematologic toxicity deemed related to study treatment must be NCI-CTCAE, v5.0 Grade ≤ 1 or equivalent severity to baseline unless deemed clinically insignificant by the investigator.

6.1.4. Premedication

Irinotecan and temozolomide should be administered following institutional-approved standard-of-care premedication guidelines. Additional premedication and supportive management for dinutuximab can be found in Section 6.5.3.

6.1.4.1. Nausea

A prophylactic treatment with anti-emetics is recommended before each treatment with irinotecan and/or temozolomide.

6.2. Preparation/Handling/Storage/Accountability

1. The investigator or designee must confirm appropriate storage conditions have been maintained during transit for all study intervention received and any discrepancies are reported and resolved before use of the study intervention.
2. Only participants enrolled in the study may receive study intervention and only authorized study personnel may supply, prepare, or administer study intervention. All study intervention must be stored in a secure, environmentally controlled, and monitored (manual or automated) area in accordance with the labeled storage conditions with access limited to the investigator and authorized study personnel.
3. The investigator or authorized study personnel is responsible for study intervention accountability, reconciliation, and record maintenance (i.e. receipt, reconciliation, and final disposition records).

4. Further guidance and information for the final disposition of unused study interventions are provided in the Pharmacy Manual.
5. Investigators should consult the study drug information provided in the label for the specific administration information (including warnings, precautions, contraindications, adverse reactions, and dose modifications).

6.3. Measures to Minimize Bias: Randomization and Blinding

This is an open-label study.

6.4. Study Intervention Compliance

Study intervention will be administered under medical supervision by the investigator or designee. The dose of study intervention and study participant identification will be confirmed prior to the time of dosing. The date and time of each dose administered will be recorded in the source documents and will be provided to the sponsor as requested.

When participants self-administer study intervention(s) at home, compliance with study intervention will be assessed at Day 1 (± 5 days) of each Cycle starting at Cycle 2. Compliance will be assessed by direct questioning, counting returned tablets/capsules, or by weighing returned granules. Compliance assessments will be documented in the source documents and CRF. When assessing compliance of granules, refer to the "Abemaciclib Oral Granules Compliance Form". Deviation(s) from the prescribed dosage regimen should be recorded in the electronic case report form (eCRF).

A record of the quantity of self-administered study intervention(s) dispensed to and returned by each participant must be maintained and reconciled with study intervention and compliance records. Intervention start and stop dates, including dates for intervention delays and/or dose reductions, will also be recorded in the CRF.

The patient must take $\geq 75\%$ of the planned doses for study treatment in a cycle to be deemed compliant unless dose holds are necessitated by AE. As outlined in Section 6.6, dose suspensions or cycle delays may occur and will not result in a patient being considered as noncompliant. A patient may be considered noncompliant if he/she is judged by the investigator to have intentionally or repeatedly taken $\geq 125\%$ of the planned doses of study treatment in a cycle. Potential discontinuation of a patient due to study drug noncompliance will be discussed between the investigator and the Lilly CRP/CRS before any determination is made to discontinue the patient.

6.5. Concomitant Therapy

With the exceptions listed in the sections below, no other chemotherapy, investigational medications, other anticancer therapy, immunotherapy, hormonal cancer therapy, herbal supplements and/or herbal drugs intended to treat cancer, radiation, or surgery for cancer will be permitted while patients are on study treatment. Palliative radiation therapy will be permitted as detailed in Section 6.5.1.

Because of a potential impact on antibody-dependent cellular cytotoxicity, any treatment with immunosuppressive activity and immunoglobulins should not be administered within 21 days

prior to Cycle 1 and for 1 week after final dinutuximab infusion. However, these medications may be allowed if medically needed to treat acute, potentially life-threatening events.

Any medication or vaccine (including over-the-counter or prescription medicines, vitamins, and/or herbal supplements) that the participant is receiving at the time of enrollment or receives during the study must be recorded along with:

- Reason for use
- Dates of administration including start and end dates

Abemaciclib is extensively metabolized through oxidation by CYP3A. In clinical drug interaction studies, coadministration of clarithromycin, a strong CYP3A inhibitor, increased exposure (area under the curve [AUC]) to abemaciclib by 3.4-fold (Study I3Y-MC-JPBE) and coadministration of rifampin, a strong CYP3A inducer, decreased exposure to abemaciclib by 95% (Study I3Y-MC-JPBF). Therefore, grapefruit or grapefruit juice, cannabis, cannabis products, and other strong inhibitors of CYP3A (see Section 10.6, Appendix 6) should not be taken during Cycle 1. Beyond Cycle 1, grapefruit or grapefruit juice, cannabis, cannabis products, as well as inducers and strong or moderate inhibitors of CYP3A should be substituted or avoided if possible (see Section 10.6, Appendix 6). The information in Appendix 6 is provided for guidance to investigators and does not preclude the use of these medications if clinically indicated.

All patients may receive supportive therapy with dexamethasone, preferably ≤ 7 days, if clinically indicated. Patients requiring more than 7 days of dexamethasone therapy will not incur a protocol deviation.

Abemaciclib can be coadministered with drugs that are substrates of CYP enzymes.

Abemaciclib and/or its major metabolites inhibit the efflux transporters P-glycoprotein and breast cancer resistance protein and renal transporters organic cation transporter 2, multidrug and toxin extrusion protein (MATE) 1 and MATE2-K at clinically relevant concentrations.

Therefore, substrates of these transporters such as metformin and those with a narrow therapeutic index such as digoxin and dofetilide should be substituted or avoided if possible.

The active metabolite of irinotecan, SN-38, is metabolized via UGT1A1. Patients receiving concomitant ketoconazole, a strong CYP3A4 and UGT1A1 inhibitor, exhibited increased exposures of irinotecan and SN-38 (Irinotecan US Package Insert 2020). Therefore, strong inhibitors of UGT1A1 (e.g. gemfibrozil, atazanavir, indinavir) should not be taken during Cycle 1. Beyond Cycle 1, strong inhibitors of UGT1A1 should be substituted or avoided if possible.

For further information regarding concomitant medications with dinutuximab, GM-CSF, irinotecan, and temozolomide refer to the guidance in each of the product labels.

Live vaccines are not permitted while on treatment and for at least 3 months after the last dose of abemaciclib. Vaccines that do not contain a live virus are permitted. Live vaccines following treatment with other study drugs should be administered according to label.

All concomitant medication administered to treat an AE or SAE must be recorded until resolution, or if events are no longer drug-related, the patient dies or is lost to follow-up, or a

new treatment is initiated. While on study, patients may be administered medications at the discretion of the investigator to treat AEs or as supportive care (e.g. anti-emetics, antibiotics).

The Lilly CRP/CRS should be contacted if there are any questions regarding concomitant or prior therapy.

